## 1.2. Schedule of Assessments

Assessment	Screen	Day 1: Surgery		Treatment Period (Hours Post End of Surgery)											End of Study/Early Termination v
	Days -28 to -1	Pre-Surgery a	Surgery	0	1	2	4	8	12	24	36	48	60	72	
Written Informed Consent b	X														
Inclusion/Exclusion Criteria c	X	X													
Medical History	X	X													
Physical Examination d	X														
Vital Signs e	X	X		X	X	X	X	X	X	X	X	X	X	X	X
Electrocardiogram f	X														X
Clinical Laboratory Testing g	X													X	X
Pregnancy Test h	X	X													X
Urine Drug Screen g	X														
COVID-19 test w	X	X w													
Adverse Events Monitoring i	←————→														
Prior/Concomitant Medications	←————→														
Pre-study personality questionnaire j	X														
C-SSRS Baseline/Screening Version Appendix J	X														

	Screen	Day 1: Surgery		Treatment Period (Hours Post End of Surgery)												End of Study/Early Termination v			
Assessment	Days -28 to -1	Pre-Surgery a	Surgery	0	1	2	4	8	12	24	36	48	60	72	Clinic Visit, Day 15 ( $\pm 2$ )				
C-SSRS Since Last Visit Version Appendix K															X	X			
Patient Health Questionnaire-9 (PHQ-9)	X																		
General Anxiety Disorder (GAD-7)	X																		
Domiciled in Clinic																			
Enrollment/ Randomization		X																	
Study Drug Dosing (XG005 or Placebo) k		X 60 min prior to surgery		Every 12 hours after the first dose defined as "Time 0" for dosing purposes only															
Blood Sample for Pharmacokinetic Assessment l		X Pre-dose			Drawn at 1, 2, 3, 4, 6, 8, 10, 12, 24, 30, 36, 42, 48, 54, 60, 66, and 72 hours ( $\pm 15$ min window) after the end of surgery (last suture) 														
Anesthesia and Bunionectomy Surgery m			X																
Continuous Pulse Oximetry n									X	X	X	X	X	X					
Rescue Medication				PRN															
Numeric Pain Rating Scale (NPRS) p,q					Measure at 0, 1, 2, 3, 4, 6, 8, 10, 12, 16, 20, 24, 30, 36, 42, 48, 54, 60, 66, and 72 hours after the end of surgery ( $\pm 10$ min window)														X (ET only)
Patient Global Assessment (PGA) of Pain Control r										X		X		X			X (ET only)		

	Screen	Day 1: Surgery		Treatment Period (Hours Post End of Surgery)											End of Study/Early Termination v					
		0	1	2	4	8	12	24	36	48	60	72								
Assessment	Days -28 to -1	Pre-Surgery a	Surgery																	
Numeric Nausea Rating Scale (NNRS) s					X		X	X	X		X		X						X (ET only)	
Sleep Interference Score (SIS) t										X		X		X					X (ET only)	
Ramsay Sedation Scale (Somnolence) u					Measure at 0, 1, 2, 3, 4, 6, 8, 10, 12, 16, 20, 24, 30, 36, 42, 48, 54, 60, 66, and 72 hours after the end of surgery ( $\pm 10$ min window)															X (ET only)
Discharge v																			X	

Abbreviations: PRN = as needed

- a) Signed informed consent must be obtained prior to a subject undergoing any study procedures or assessments.
- b) Subject's must meet all of the study inclusion criteria as shown in [Section 5.1](#) and none of the exclusion criteria as shown in [Section 5.2](#). All inclusion and exclusion criteria must be verified by the Investigator or designee at Screening (Day -28 to Day -1) and Pre-Surgery (Day 1).
- c) All Pre-surgery assessments to be performed within 24 hours prior to surgery. For inclusion/exclusion criteria and medical history only, assess updates since Screening and evaluate for continued eligibility. The Investigator or designee may repeat lab tests and vitals/ECGs prior to randomization.
- d) A PE will be obtained at Screening. A complete physical examination will include assessments of the head, eyes, ears, nose, throat, skin, neck (including thyroid), lungs, cardiovascular, abdomen, lymph nodes and extremities. The subject's height and weight will be measured to determine body mass index at Screening to determine eligibility. It is not necessary to collect information regarding well-healed surgical scars or tattoos. If abnormalities are noted during the Screening, they should be also recorded on the Adverse Event eCRFs or Medical History, as appropriate. Subjects will be advised at Screening that if they terminate the study prior to 72 hours, it is requested that they remain in the clinic for continued collection of scheduled safety data only.
- e) Vital signs (blood pressure [systolic/diastolic], heart rate, respiratory rate, oral body temperature) will be collected from all subjects at Screening, before the first dose Pre-Surgery ( $\pm 10$  minutes) and Hours 0, 1, 2, 4, 8, 12, 24, 36, 48, 60, and 72, and Day 15/Early Termination ( $\pm 10$  minutes). Monitoring of continuous pulse oximetry begins at Hour 0 (start of the domiciling period). Vital signs may be obtained at any other times as deemed necessary by the Investigator. Vital signs throughout the study should be obtained supine after resting for approximately 5 minutes. Automated blood pressure machines may be used to standardize measurements. Body temperature will be determined by obtaining oral temperature ( $^{\circ}$ C).
- f) 12-lead ECG data will be collected from all subjects at Screening and at the Day 14 clinic visit, and from any subject who is determined to be exhibiting any relevant abnormality per the discretion of the investigator. 12-lead ECGs will be obtained at each time point using an ECG machine that automatically calculates the heart rate and measures PR, QRS, QT, and QTc intervals. QTcF will also be calculated. 12-lead ECGs will be measured in the supine position, after the subject has been supine for at least 10 minutes.
- g) Clinical laboratory parameters include standard **chemistry** (albumin, total bilirubin, total protein, calcium, alkaline phosphatase, alanine aminotransferase [ALT], aspartate aminotransferase [AST], blood urea nitrogen [BUN], creatinine, glucose, sodium, potassium, chloride, bicarbonate, lactate dehydrogenase

[LDH], and uric acid; **hematology** (HbA1c [Screening only], hemoglobin, hematocrit, red blood cell [RBC] count, RBC indices, mean corpuscular hemoglobin [MCH], mean corpuscular hemoglobin concentration [MCHC], platelet count, and white blood cell [WBC] count including differential; coagulation panel (prothrombin time [PT], partial thromboplastin time [PTT], and fibrinogen); **serology** (human immunodeficiency virus [HIV] antibody, hepatitis B virus surface antigen, hepatitis B anti-core antibody (anti-HBc) and anti-surface antibody, and hepatitis C virus antibody); **urinalysis** (pH, specific gravity, blood and leukocyte esterase, glucose, protein, and ketones), and **urine drug screen** (amphetamines, barbiturates, benzodiazepines, cocaine, opiates, phencyclidine [PCP], tetrahydrocannabinol [THC], methamphetamine, methadone, and ecstasy).

- h) For premenopausal women, a serum pregnancy test will be conducted at Screening visit, a urine pregnancy test will be conducted pre-surgery on Day 1 and at Exit Visit. Premenopausal women must have a negative serum pregnancy test to be included in study. Results must be available before surgery.
- i) Reporting of treatment-emergent AEs begins at the time of first dose of study drug and ends 30 days after the last dose of study drug. Non-treatment emergent AE reporting begins at Screening after signing of ICF until the first dose of study drug is administered.
- j) Subjects will be assessed at Screening on their potential placebo response by use of a pre-study personality questionnaire ([Appendix B](#)). This is a exploratory analysis for information purposes only.
- k) Study drug will be administered 60 minutes prior to start of surgery and every 12 hours for 72 hours after the time of first dose. The clock time of first dose is noted as “Time 0”, and it will be recorded to facilitate the PK analyses.
- l) Blood draws will always be performed after NPRS assessment and prior to the first administration of rescue medication. Considering the surgery time may largely vary among subjects, the PK sampling plan used the post-end-of-surgery schedule to be consistent with the efficacy assessment schedule. Each subject in the PK group (one site only) will have blood samples collected for PK assessments at predose and at the following intervals post-surgery (last suture) 1, 2, 3, 4, 6, 8, 10, 12, 24, 30, 36, 42, 48, 54, 60, 66, and 72 hours ( $\pm 15$  min window). XG005, naproxen, and pregabalin concentrations in plasma will be measured. The actual clock time when the PK sample is collected will be recorded, and the post-dose time for PK analysis will be calculated based on the recorded clock time. All subjects will have blood samples collected for PK assessments at any time in which a subject is determined to be exhibiting any relevant abnormality per the discretion of the investigator.
- m) Subjects will undergo primary, unilateral, first metatarsal Austin bunionectomy. The surgical procedure should be limited to a maximum duration of 90 minutes. End of surgery will be defined as completion of the last suture.
- n) Subjects will be on continuous pulse oximetry monitoring throughout the confinement period but, absent a respiratory AE, oxygen saturation ( $SpO_2$ ) will be recorded every 12 hours post-end of surgery.
- o) Subjects will be permitted rescue medication throughout the 72-hour inpatient domiciling period as follows to manage breakthrough pain only if it occurs while domiciled: IV acetaminophen 1 g, will be administered Q 6 hours, PRN, up to 4 g in 24 hours. If a patient is unable to tolerate acetaminophen or if there is insufficient pain relief, 50 mg tramadol will be administered Q 4 hours, PRN, up to 300 mg in 24 hours. Study staff will record the time and the dose of rescue medication administered on the rescue medication form. NPRS and PK sampling will be collected immediately prior to administering rescue medication. Only the protocol-defined rescue medication is permitted in the study.
- p) Study staff will record subject-reported pain assessments via a standard 11-point NPRS at the following time points post-end of surgery: 0, 1, 2, 3, 4, 6, 8, 10, 12, 16, 20, 24, 30, 36, 42, 48, 54, 60, 66, and 72 hours within a  $\pm 10$ -minute window ([Appendix C](#)). NPRS will be collected prior to PK sampling and administration of rescue medication.
- q) Pain intensity assessments scheduled between 24:00 and 06:00 may be skipped if the subject is sleeping. However, consecutive pain assessments may not be skipped, and the Hour 12, Hour 24, and Hour 48 pain assessments must be completed even when they fall asleep between 24:00 and 06:00.
- r) Study staff will record subject-reported PGA of pain control using a 5-point scale (poor, fair, good, very good, excellent) at the following time points post-end of surgery: 24, 48, and 72 hours within a  $\pm 10$ -minute window and just prior to receiving a dose of rescue medication ([Appendix D](#)). PGA will also be performed and recorded at early termination.

- s) Nausea will be measured after the end of surgery by using the 11-point NNRS at the indicated time points with a  $\pm$  10-minute window ([Appendix E](#)). PK sampling blood draws will always be performed after NNRS assessment. Additional NNRS time points will be collected when an AE of nausea or vomiting is reported or prior to any rescue antiemetic medication. Administration of antiemetic medications are limited to subjects with active vomiting, subjects with a score  $\geq 5$  on the NNRS, or by subject request only. No pretreatment for potential nausea and vomiting is permitted.
- t) Sleep Interference Score using the 11-point NRS scale (0=no interference to sleep, 10=worst interference imaginable) to be assessed at 24, 48 and 72 hours post-surgery within a  $\pm 15$ -minute window.
- u) Ramsay Sedation Scale to be determined by observation of subject by study staff when NPRS is assessed (Footnote p, above).
- v) Subjects will be discharged at a reasonable hour of the day after the end of the 72-hour treatment period, which may include the morning after the end of the 72-hour treatment period. Early termination visits will include the following assessments: NPRS, PGA, NNRS, SIS, and safety assessments (vital signs, ECG, laboratory testing, and concomitant medications).
- w) All subjects will be tested for COVID-19 during Screening and within 3 days prior to surgery. COVID-19 testing samples will be taken prior to surgery on Day 1 from subjects that are in the PK sampling groups. The result of that test is not necessary before surgery.

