
 
To evaluate rescue medication consumption at 24, 48, and 72 hours, time to first use of rescue medication from end of surgery, and proportion of subjects requiring rescue medication.
 
To evaluate nausea assessment scores at various timepoints.
 
To evaluate high and low dose XG005 compared to placebo for SIS
 
	
 
Total oral opioid rescue medication consumption at 24, 48, and 72 hours
 
Nausea (NNRS) assessment scores at 1, 4, 8, 12, 24, 48, 72 hours
 
SPI at 0, 1, 2, 3, 4, 6, 8, 10, 12, 16, 20, 24, 30, 36, 42, 48, 54, 60, 66, and 72 hours
 
Pain intensity at various timepoints
 
SIS at 24, 48 and 72 hours
 
Percentage of subjects requiring rescue at various timepoints
 
PGA of pain control at various timepoints
 
Ramsay Sedation Scale at various timepoints
 

Objectives	Endpoints

 
Exploratory purposes only: To estimate subject's potential placebo response by use of a pre-study personality questionnaire at Screening.
 
	
 
Estimated of subject susceptibility to placebo response at Screening using a pre-study personality questionnaire
 

Safety:	

 
To evaluate the safety and tolerability of XG005 in a perioperative population
 
	
Safety and tolerability of XG005 compared with placebo measured:
 
 
The incidence, intensity, relationship, and seriousness of TEAEs by treatment group.
 
The number and percentage of premature withdrawals due to AEs in each treatment group.
 
Treatment-emergent changes in vital signs (blood pressure, heart rate, body temperature, respiratory rate, continuous pulse oximetry) and Sp02 after each Treatment Period dose and the Follow-up Visit compared to Baseline values.
 
Treatment-emergent changes in clinical laboratory tests and ECGs compared to Baseline.
 

Pharmacokinetics	

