#### 4.3. Justification for Dose

In this study, the subjects will be randomized in a 1:1:1 ratio to receive one of two doses of XG005, or placebo. The two doses of XG005 are selected based on the plasma levels of naproxen and pregabalin previously associated with analgesic efficacy ([Lyrica®](#) (Pregabalin) Prescribing Information. (June 2011) Pfizer Inc., US.; [Naprosyn®](#) (naproxen sodium) Prescribing Information. (November 2017) Atnahs Pharma Australia Pty Ltd.; [Bockbrader HN](#),

Naproxen is rapidly and completely absorbed from the GI tract with an *in vivo* bioavailability of 95%. The elimination half-life of naproxen ranges from 12 to 17 hours. Steady-state levels of naproxen are reached in 4 to 5 days. Following oral administration of naproxen 500 mg tablets,  $C_{max}$  of 71,100 ng/mL,  $T_{max}$  of 2.3 hours, and  $AUC_{0-t}$  of 1,218,000 ng.hr/mL were observed. Similar AUC and 30% lower  $C_{max}$  of naproxen were produced by oral administration of 1000 mg of XG005 tablet (4  $\times$  250 mg XG005 tablets). In general, the clinical recommended dose ranges are 220 mg-1500 mg of naproxen for the various pain symptoms.

Two dose levels are planned in this study:

- 1) XG005 (low dose) with 750 mg XG005 BID which will deliver 375 mg BID of naproxen and 259 mg BID of pregabalin.
- 2) XG005 (high dose) with 1250 mg XG005 BID which will deliver 626 mg BID of naproxen and 433 mg BID of pregabalin.

Based on the PK modeling, 1250 mg XG005 BID will be equivalent to the exposure of naproxen at 490 mg BID and the exposure to pregabalin of 225 mg BID; 750 mg XG005 BID will result in bioequivalent to naproxen of 300 mg BID and pregabalin of 150 mg BID. So, the planned XG005 dose regimen would provide naproxen dose within the commonly prescribed dose for treating various pain indications. Pregabalin has been approved for maximum dose of 600 mg/day, though with 150 mg/day starting dose, in approved pain indications. Phase 1 studies in healthy volunteers from XG005 including dose of 1250 mg BID resulted in acceptable safety profile, with similar dizziness and somnolence incidences as reported in Lyrica label. Patient's safety will be carefully monitored in the study.

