### 8.2. Safety Assessments

The timing and frequency of all safety assessments are provided in the SOA ([Section 1.2](#)). Safety endpoints include monitoring and recording of AEs and SAEs, clinical laboratory results (serum chemistry, hematology, coagulation, and urinalysis), 12-lead ECG results, and vital signs measurements (blood pressure [systolic and diastolic], heart rate, respiratory rate, oral body temperature, and continuous pulse oximetry), and recording of relevant safety data.

Trained staff on hand in the research unit will monitor respiratory safety via respiration rate, continuous pulse oximetry and oxygen saturation ( $\text{SpO}_2$ ) checks every 12 hours post-end of surgery within a  $\pm 10$ -minute window, and somnolence if observed by Staff at times other than

when a formal assessment of somnolence is scheduled. The Ramsay Sedation Scale (RSS, [Appendix G](#)) will be used as an assessment of sedation (somnolence) with the same time sequence as the NPRS determination, but with a window of  $\pm 15$  minutes. A Columbia-Suicide Severity Rating Scale since last visit ([Appendix K](#)) will be administered at 72 hours post treatment and at the follow-up visit and at the end of study visit/early termination visit.

For all safety assessments, the investigator will determine whether results are clinically significant, which is defined as any variation in a result that has medical relevance and that may result in an alteration in medical care (e.g., active observation, diagnostic measures, or therapeutic measures). If clinical significance is noted, the result and reason for significance will be documented and an AE reported on the AE page of the subject's electronic case report form (eCRF). The investigator will monitor the subject until the result has reached the reference range or the result at Screening, or until the investigator determines that follow-up is no longer medically necessary.

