### **9.5.3. Safety Analyses**

Adverse events will be coded by preferred term and system organ class (SOC) using the latest version of MedDRA (version 23 or higher). All AE data will be presented in a data listing. Treatment-emergent AEs will be summarized by treatment and overall, as well as by severity and relationship to study drug. Serious AEs and AEs leading to discontinuation of study drug will also be presented in the data listings and summarized by treatment and overall.

Actual values and changes from baseline for clinical laboratory test results, vital sign measurements, and 12-lead ECG results will be summarized by treatment at each time point using descriptive statistics (number of subjects, mean, SD, median, minimum, and maximum). Shift tables will be generated for clinical laboratory test results. Physical examination findings will be presented in a data listing.

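### Routine 12-lead ECGs fall 9 to 13.5 days after the last dose, so for completers the by-treatment ECG change describes off-drug values

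*Combined protocol and SAP*

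**What the plan says.** - **Timing.** Section 8.2 hands timing to the Schedule: "The timing and frequency of all safety assessments are provided in the SOA". The Schedule's ECG row is marked at Screening and in the End of Study/Early Termination column, with nothing from pre-surgery to Hour 72. Footnote f gives the same two routine occasions: "12-lead ECG data will be collected from all subjects at Screening and at the Day 14 clinic visit".
- **Visit day.** The Schedule heads the last column "Clinic Visit, Day 15" with a window of ±2 days. Footnote e ("48, 60, and 72, and Day 15/Early Termination") and section 4.1 also use Day 15. Only footnote f says Day 14.
- **Endpoint.** The Safety part of section 3 lists "Treatment-emergent changes in clinical laboratory tests and ECGs compared to Baseline". The neighbouring bullet, on vital signs and SpO2, goes further and asks for changes "after each Treatment Period dose and the Follow-up Visit compared to Baseline values".
- **Analysis.** Section 9.5.3 covers actual values and changes from baseline: "12-lead ECG results will be summarized by treatment at each time point".
- **Other ECGs.** Footnote c allows repeats before randomization, which are pre-drug. Footnote f adds ECGs when the investigator sees a relevant abnormality. Early terminators have an ECG at termination, and section 7.4 also lists ECGs among the assessments continued during their requested 72-hour stay.

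**The concern.** The plan presents ECG change as a treatment-emergent safety measure and tabulates it by arm. For a subject who completes the study, the only routine post-baseline ECG is taken long after dosing has ended. The three arms are then compared when none has meaningful naproxen exposure. A lasting change could still be seen. A change that reverses when the drug clears could not, and a flat table might be read as evidence of no effect during treatment. Footnote f asks for PR, QRS, QT, QTc and QTcF, so interval data are wanted, but the schedule does not collect them routinely during exposure. Laboratory tests share the ECG's endpoint bullet, yet they do have an Hour 72 sample.

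**Working it through.** The plan gives no figure of its own to reproduce here. The check is study-day arithmetic.

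**Inputs**
- First dose on Day 1, taken as 0 h, then every 12 hours for 72 hours (section 1.2, footnote k; section 6.2). The wording does not settle whether a dose is given at 72 h, so the last dose is at 60 h (six doses) or 72 h (seven doses).
- Final visit Day 15 ±2, so Days 13 to 17 (Schedule).
- Section 4.3: "The elimination half-life of naproxen ranges from 12 to 17 hours". The documents give no half-life for pregabalin or XG005, so 6 to 24 h is assumed.
- Dose-to-surgery interval: 60 ± 10 minutes (Synopsis) or within 60 minutes (section 4.1). Surgery lasts at most 90 minutes (section 6.5.5).
- Tmax about 4 hours (section 4.2). 150 subjects randomized per arm (section 5.5).

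**1. Gap from last dose to routine ECG.** Gap = (visit day − 1) × 24 − last dose time, assuming the visit is at the same clock time as the first dose.
- Shortest: (13 − 1) × 24 − 72 = 288 − 72 = 216 h = 9.0 days.
- Nominal: 336 − 72 = 264 h = 11.0 days, or 336 − 60 = 276 h = 11.5 days.
- Longest: (17 − 1) × 24 − 60 = 384 − 60 = 324 h = 13.5 days.
- If the visit may be up to 10 h earlier or later in the day (assumption), the ends become 206/24 = 8.6 and 334/24 = 13.9 days.
- Footnote f's Day 14 taken literally: 312 − 72 = 240 h to 312 − 60 = 252 h, or 10.0 to 10.5 days. This lies inside the range above.

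**2. Drug remaining at the shortest gap.** Fraction of the last dose = 0.5^(gap / half-life).
- Naproxen, 17 h: 216/17 = 12.71 half-lives; 0.5^12.71 = 0.00015, or 0.015%.
- Naproxen, 12 h: 216/12 = 18 half-lives, less still.
- Naproxen at 17 h, summing all seven doses: r = 0.5^(12/17) = 0.613; (1 − r^7)/(1 − r) = 2.50; 2.50 × 0.015% = 0.037% of one dose.
- Pregabalin or XG005 at the assumed 6 to 24 h: 36 to 9 half-lives. At 24 h, 0.5^9 = 0.2% of the last dose.

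**3. Who is affected.** 2 × 150 = 300 subjects planned for XG005, and 150 placebo comparators. Routine on-drug ECGs planned: none.

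**4. Where an Hour 72 ECG would fall.** Hour 72 counts from the end of surgery.
- Synopsis interval: first dose to end of surgery is 50 to 70 min plus 0 to 90 min, or 0.83 to 2.67 h.
- Section 4.1 interval: 0 to 60 min plus 0 to 90 min, or 0 to 2.50 h.
- Taken together: 0 to 2.67 h, so Hour 72 is 72.0 to 74.7 h after the first dose. The zero end is a bound, since it would need an operation of no length.
- That is 0 to 2.7 h after a 72-h dose, or 12.0 to 14.7 h after a 60-h dose.
- In the later case, at the shorter naproxen half-life, 14.7/12 = 1.2 half-lives, against at least 12.7 under the present schedule. Hour 72 is on drug under either reading.

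**The case against.** The best defence is that sparse ECGs are a legitimate choice. The ECG summary is descriptive, with no hypothesis test. Section 3 promises only a comparison with Baseline, so the endpoint as written can be delivered. The treatment-emergent AE window runs to 30 days after the last dose, so a Day 15 ECG lies inside it. Vital signs are taken at 11 post-surgery time points, pulse oximetry is continuous, and a relevant abnormality triggers an ECG. Section 7.1 reports no adverse events of special interest in three Phase 1 trials. Whether on-drug ECGs were taken in those trials cannot be judged from these documents.

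Much of this stands. It rules out two stronger readings that a reader might infer. The first is that section 3 contradicts the Schedule. It does not: measurement after each dose is promised for vital signs and SpO2, not for ECGs. The second is that subjects face a known cardiac risk. The documents report no ECG signal.

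The defence does not restore the comparison. A 30-day AE window classifies events; it does not make a Day 15 tracing an on-drug one. Heart rate and blood pressure do not measure PR, QRS or QT. Triggered and early-termination ECGs may be on drug, but they come from a selected subset that can differ by arm, so they do not support a randomized comparison.

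It is also fair to say that Hour 72 is not an ideal time. It falls before the roughly 4 h Tmax after a 72-h dose, or about one dosing interval after a 60-h dose.

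**Conclusion.** The point holds as a limit on what the planned table can show, and as a cheap improvement. For completers, the routine by-treatment ECG change rests on values taken 9 to 13.5 days after the last dose. It cannot reveal a reversible on-drug effect, although a persistent one could still appear.

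The conclusion rests on nominal visit days, on a last dose at 60 or 72 h, and on the section 4.3 naproxen half-life applying to naproxen released from XG005. For pregabalin and XG005 it rests on the assumed 6 to 24 h. Plausible shifts in visit clock time do not change it.

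A reader might make more of Day 14 against Day 15. Day 14 lies inside the ±2 window, so that mismatch is editorial. Section 7.4 is a separate mismatch on ECG timing: it lists ECGs during the early terminators' 72-hour stay, while the Schedule has none at Hours 0 to 72.

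**What to change.** 1. In the Schedule, mark the routine post-dose 12-lead ECG at Hour 72, when subjects are still domiciled and vital signs and laboratory samples are already taken. Change the End of Study mark to early termination only.
2. Revise footnote f to match, which also removes its stray Day 14. Keep the investigator-triggered ECGs.
3. Align section 7.4 with the revised Schedule on ECGs during the 72-hour stay.
4. Reconcile the passages on whether a 72-h dose is given, because that sets whether Hour 72 falls up to about 2.7 h after a dose or about 12 to 14.7 h after one.

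Section 9.5.3 needs no change, since it already summarizes at each time point.

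**Cost.** Two table cells, one footnote and an edit to section 7.4, with no additional routine ECG if it is moved. The routine late ECG is lost; keeping it as well adds up to 450 ECGs, and footnote f's visit day would then have to be made to agree with the Schedule. Hour 72 may miss the Tmax, so a peak effect could be underestimated. If the schedule is left as it is, the limitation should at least be stated beside the ECG summary.
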